8 STUDY ASSESSMENTS AND FLOW CHART

8.1 Efficacy Measurements

Primary Efficacy Variable:

Duration of diarrhea (hours) between the start of treatment until last diarrheal/watery stool before recovery or end of study treatment (treatment duration maximal 5 days). Treatment will stop at recovery or after the morning dose of day 6, if not recovered.

Duration of diarrhea is defined by date and time of the evacuation of the final diarrheal stool derived from the daily diary.

Secondary Efficacy Variables:

- Time until recovery, defined by date and time of the evacuation of the first of two consecutive normal stools or no stool within 12 hours.
- Number of recovered subjects per treatment group in total and until each individual treatment day. Mean and median time until recovery per treatment group.
- Global Physician Assessment at the end of treatment:
 - 1 = Complete relief of acute diarrhea,
 - 2 = marked improvement of acute diarrhea,
 - 3 = moderate improvement of acute diarrhea,
 - 4 = slight improvement of acute diarrhea,
 - 5 = no change in acute diarrhea,
 - 6 = worsening of acute diarrhea. (Treatment success = GPA score of 1 or 2).
- For toilet trained children and adolescents: number of stools per day as well as number of watery stools per day from start of treatment and until end of study treatment.

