Subjects will be treated with Racecadotril tid according to the body weight dose requirement on an in- or out-patient basis for maximum 5 days. One arm will be treated with ORS alone as standard treatment, the other treatment arm will be treated with ORS (according to the registered local label and the instruction of the investigator) in addition to Racecadotril. ORS will be prescribed by the investigator and will be taken according to the product label and the instruction of the investigator(s) will be instructed to stop study drug treatment when the patient recovered. On each day, the parent(s)/caregiver(s) will fill in their diaries, documenting the date and time of each individual stool, the stool consistency of each stool (diarrheal/watery or normal), the amount of ORS and the study drug intake. After the occurrence of two consecutive normal stools, the parent(s)/caregiver(s) can stop recording of the diary and return to the study site for the end of treatment visit. The date of recovery is the day when the first of two consecutive normal stools were excreted. AEs are to be reported on an ongoing basis.

End of treatment (Day 6 or early recovery, Visit 2)

The last dose of study drug will be the morning dose of day 6, if not recovered earlier. The same day, or within 24 hours after recovery, the parent(s)/caregiver(s) will visit the site for the end of treatment visit of the child. Data on vital signs, AEs, physical examination and concomitant medication will be collected. Subjects will return their diaries and unused medication.

Safety follow-up

A phone call will be performed at 5-7 days after end of the treatment period for the safety follow-up.

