3.3 Study Objectives

Primary Objective(s)

The primary objective is to evaluate the efficacy of Racecadotril in addition to standard treatment oral rehydration solution (ORS) versus ORS alone in infants, children and adolescents (3 months until <18 years) with acute diarrhea measured as duration of diarrhea (hours) between the start of treatment until final diarrheal/watery stool before recovery or end of study treatment (treatment duration maximal 5 days).

Duration of diarrhea is defined by date and time of the evacuation of the final watery/diarrheal stool before recovery derived from the daily diary (see Figure 3-2 Duration of diarrhea and Time until recovery definition).

First dose of study

Figure 3-2 Duration of diarrhea and Time until recovery definition

Secondary Objective(s)

- Number of recovered subjects per treatment group in total and until each individual treatment day. Mean and median time until recovery per treatment group.
- Time until recovery, defined by date and time of the evacuation of the first of two consecutive normal stools or no stool within 12 hours after first normal stool (see Figure 3-2 Duration of diarrhea and Time until recovery definition).
- Global Physician Assessment at the end of treatment:
 - \circ 1 = Complete relief of acute diarrhea,
 - \circ 2 = marked improvement of acute diarrhea,

- \circ 3 = moderate improvement of acute diarrhea,
- 4 =slight improvement of acute diarrhea,
- \circ 5 = no change in acute diarrhea,
- \circ 6 =worsening of acute diarrhea. (Treatment success = GPA score of 1 or 2).
- For toilet trained children and adolescents: number of stools per day as well as number of watery stools per day from start of treatment and until end of study treatment.

Safety Objective(s)

To evaluate the safety and tolerability of Racecadotril together with oral rehydration solution (ORS) versus ORS alone in infants, children and adolescents with acute diarrhea by adverse events, physical examination and vital signs.

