4.2.1 Primary Efficacy Analysis

The primary efficacy variable is the duration (hours) of diarrhea (treatment duration max 5 days). Duration of diarrhea is defined by date ("event" date) of the evacuation of the last diarrheal/watery stool before recovery.

In order to compare the primary efficacy parameter, duration of diarrhea, between the treatment groups, a Kaplan Meier (KM) analysis will be performed. The KM algorithm will be applied to derive the median duration and the 95% confidence intervals for the median, Q1, Q3 and mean duration with Greenwood's estimator of standard deviation of Kaplan-Meier estimator.

The log-rank test will be used to test whether the difference between the duration of diarrhea between two treatment groups is statistically significant, i.e. p-value <0.05.

For duration estimation the date and time of first drug intake will be assumed as start time point and all subjects without "event" will be censored by 6 days (144 hours).

SAS code for the analysis:

PROC LIFETEST DATA = [dataset name] METHOD=KM PLOTS=SURVIVAL OUTSURV=SURV CONFTYPE=LOGLOG ATRISK; TIME [time variable]*[censor variable]; STRATA [arm variable];

RUN;

The "OUTSURV=SURV" statement provides variables that contains the lower and upper limits of the pointwise confidence intervals for the survivor function ("SDF_LCL" and "SDF_UCL"), this confidence intervals should be transformed for tables as follows:

[Lower limit var name] = round(100*(1-SDF_UCL),.1); [Upper limit var name] = round(100*(1-SDF_LCL),.1);

As a first sensitivity analysis, duration of diarrhea will be analyzed by age subgroups as follows:

- Racecadotril + ORS (age subgroup 3 to < 24 month) vs ORS (age subgroup 3 to < 24 month) comparison;
- Racecadotril + ORS (age subgroup >= 2 to <12 years) vs ORS (age subgroup >= 2 to <12 years) comparison;
- Racecadotril + ORS (age subgroup 12 to < 18 years) vs ORS (age subgroup 12 to < 18 years) comparison;

As a second sensitivity analysis, duration of diarrhea will be analyzed by weight/dosing subgroups as follows:

• Racecadotril + ORS (Infants less than 9 kg) vs ORS (Infants less than 9 kg) comparison;

- Racecadotril + ORS (Infants from 9 kg to < 13 kg) vs ORS (Infants from 9 kg to < 13 kg Infants from 9 kg to < 13 kg) comparison;
- Racecadotril + ORS (Children from 13 kg to 27 kg) vs ORS (Children from 13 kg to 27 kg) comparison;
- Racecadotril + ORS (Children from more than 27 kg to 60 kg) vs ORS (Children from more than 27 kg to 60 kg) comparison;

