4.2.2 Secondary efficacy analysis

The secondary efficacy variables are

- Number of recovered subjects per treatment group in total and until each individual treatment day. Mean and median time until recovery per treatment group.
- Time until recovery, defined by date and time of the evacuation of the first of two consecutive normal stools.

Time until recovery, number of recovered subjects per treatment group in total and until each individual treatment day and mean and median time until recovery per treatment group will be estimated Kaplan Meier analysis as described for the primary endpoint.

- Global Physician Assessment at the end of treatment:
 - \circ 1 = Complete relief of acute diarrhea,
 - \circ 2 = marked improvement of acute diarrhea,
 - \circ 3 = moderate improvement of acute diarrhea,
 - 4 =slight improvement of acute diarrhea,
 - \circ 5 = no change in acute diarrhea,
 - \circ 6 = worsening of acute diarrhea.

Frequencies table will be performed for the Global Physician Assessment at the end of treatment by GPA score and by success rating. Treatment will be rated as success when the GPA score equals 1 or 2.

Description of the subgroup analysis is presented in the Section 4.2.3 of the SAP.

The comparisons of treatment arms using Fisher exact test will be performed by proportion of patients with Global Physician Assessment success at the end of treatment.

SAS code for the analysis:

PROC FREQ DATA = [dataset name]; WEIGHT [GPA frequency] / ZEROS; TABLES [GPA yes/no level] * [Arm] / EXACT FISHER;

RUN;

If SAS code produces the "Row or column sum zero. No statistics computed for this table." output due to insufficient memory available to complete the Fisher exact computations, then the p-value should be assumed as equal 1.0000.

• For toilet trained children and adolescents: number of stools per day as well as number of watery stools per day from start of treatment and until end of study treatment.

Number of stools and number of watery stools will be presented descriptively per treatment group and cumulatively until each day of treatment.

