NST028	Subject Status	10.1.4.1.6.7	Duration of diarrhea. Descriptive statistics (in hours) and comparison results for weight/dosing category children from more than 27 kg to 60 kg – Per Protocol Subject Sample			
NST029	Subject Status	10.1.4.1.6.8	Duration of diarrhea. Descriptive statistics (in hours) and comparison results for weight/dosing category children or adolescents of 60 kg or higher – Per Protocol Subject Sample			

				Produced	for:	
Output Code	Clinical Domain	Output Number	Title	Headline Results	SMT	Interim Analysis
NST030	Subject Status	10.1.4.1.6.9	Duration of diarrhea. Number of stools during the study - Per Protocol Subject Sample			
NST031	Subject Status	10.1.4.1.7	Number of stools per day (toilet trained subgroup) – Full Analysis Subject Sample			
NST032	Subject Status	10.1.4.1.8	Number of watery stools per day (toilet trained subgroup) – Full Analysis Subject Sample			
NST033	Subject Status	10.1.4.1.9	Cumulative number of stools until recovery or end of treatment by days – Full Analysis Subject Sample			
NST034	Subject Status	10.1.4.2.1	Time to recovery: time to evacuation of the first of two consecutive normal stools or no stool after first normal stool within 12 hours by days. Kaplan-Meier analysis – Full Analysis Subject Sample			
NST035	Subject Status	10.1.4.2.2.1	Time to recovery. Descriptive statistics (in hours) and comparison results – Full Analysis Subject Sample			
NST036	Subject Status	10.1.4.2.2.2	Time to recovery. Descriptive statistics (in hours) and comparison results – Full Analysis Subject Sample			
NST037	Subject Status	10.1.4.2.2.3	Time to recovery. Descriptive statistics (in hours) and comparison results for age group from 3 to < 24 month – Full Analysis Subject Sample			
NST038	Subject Status	10.1.4.2.2.4	Time to recovery. Descriptive statistics (in hours) and comparison results for age group from >= 2 to <12 years – Full Analysis Subject Sample			
NST039	Subject Status	10.1.4.2.2.5	Time to recovery. Descriptive statistics (in hours) and comparison results for age group from 12 to < 18 years – Full Analysis Subject Sample			

				Produced	for:	
Output Code	Clinical Domain	Output Number	Title	Headline Results	SMT	Interim Analysis
NST040	Subject Status	10.1.4.2.2.6	Time to recovery. Descriptive statistics (in hours) and comparison results for weight/dosing category Infants less than 9 kg – Full Analysis Subject Sample			

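### A child whose watery stools stop and who passes no further stool before the diary ends has no recovery and no primary event under the SAP, and is censored at 144 h as still ill

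*SAP*

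**What the plan says.** The primary event in SAP 4.2.1 is the "evacuation of the last diarrheal/watery stool before recovery". Without a recovery there is no event, and "all subjects without 'event' will be censored by 6 days (144 hours"). SAP 4.2 excludes imputation.

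The SAP states recovery in four places, each of which starts from a normal stool:

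- SAP 3.1: "The date of recovery is the day when the first of two consecutive normal stools were excreted".
- SAP 3.3: "first of two consecutive normal stools or no stool within 12 hours after first normal stool".
- SAP 4.2.2: "Time until recovery, defined by date and time of the evacuation of the first of two consecutive normal stools".
- SAP 9.2.1, title of Table 10.1.4.2.1 (repeated in 9.3.1): "first of two consecutive normal stools or no stool after first normal stool within 12 hours".

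Protocol 8.1 has "first of two consecutive normal stools or no stool within 12 hours", without saying that a normal stool must come first. The protocol synopsis objectives and section 3.2 agree with it. Elsewhere the protocol gives only the two-normal-stools rule: synopsis methodology, synopsis criteria for evaluation, 4.1 and 10.3. SAP section 7, on changes to planned analyses, lists none.

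SAP 3.3 also lets the primary duration run to the final watery stool before recovery or before the end of study treatment. SAP 4.2.1 does not carry that second alternative.

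**The concern.** Diarrhea can end with a formed stool or with no stool for a day or two. The SAP recognises only the first. In the second case the illness is over, yet the child carries the longest possible value on the primary endpoint and counts as unrecovered on time until recovery. The 144 h value also lies beyond anything observed, because the diary is collected at the Day 6 visit.

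The loss is not random. The later the diarrhea ends, the less diary time remains in which to record a normal stool, so the slower arm loses more. If an antisecretory drug lengthens the stool-free gap, the loss instead falls more on racecadotril.

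**Working it through.** **The rules applied to one record.** This is a constructed example: watery stools at 4, 12, 21, 31, 41, 51, 61 and 70 h after first dose, then no stool until the diary ends at 116 h. No gap before 70 h exceeds 10 h; the final gap is 46 h.

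- SAP 3.1 and 4.2.2: no normal stool, so no recovery; censored at 144 h.
- SAP 3.3 and the table titles: no first normal stool from which to count 12 h; censored at 144 h.
- Protocol 8.1 read literally: recovered; duration 70 h.
- SAP 3.3 with the end-of-treatment alternative: duration 70 h.

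**Inputs for the size.** Recovery percentages and 55 per group come from Protocol 10.8. Control is 18.3, 35.8, 59.4, 76.3 and 80.6% at 24, 50, 72, 96 and 120 h; racecadotril is 46.6, 70.1, 84.2, 90.1 and 94.7%. I interpolated linearly. The rest is assumed:

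- The diary ends at 116 h for a noon start (12:00 on Day 1 to 08:00 on Day 6, 5×24−4) or 110 h for an evening start (18:00 to 08:00, 5×24−10), in equal mix.
- The gap from last watery stool to next stool is lognormal with median m and log-SD 0.6.
- A child whose diarrhea ends at t, with diary end D, is lost when D−t ≥ 12 and the gap exceeds D−t. For D−t ≥ 12 the probability is 1−Φ(ln((D−t)/m)/0.6).

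**Step 1: the protocol's own figures.** Control median: 50 + 22×(50−35.8)/(59.4−35.8) = 63.2 h (stated 64). Racecadotril median: 24 + 26×(50−46.6)/(70.1−46.6) = 27.8 h (stated 28). Difference at 120 h: 94.7−80.6 = 14.1 points. Control upper quartile: 72 + 24×(75−59.4)/(76.3−59.4) = 94 h.

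**Step 2: losses and the 120 h difference.**

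| Median gap | Lost, control | Lost, racecadotril | Difference at 120 h |
|---|---|---|---|
| 12 h | 2.8% | 1.2% | 94.7×0.988 − 80.6×0.972 = 15.2 |
| 18 h | 7.5% | 3.2% | 94.7×0.968 − 80.6×0.925 = 17.1 |
| 24 h | 13.4% | 6.1% | 94.7×0.939 − 80.6×0.866 = 19.1 |

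Losses are percentages of subjects whose diarrhea ended within 120 h. With log-SD 0.8 and median 24 h they are about 17% and 10%. Counting only children with at least 24 stool-free hours, at log-SD 0.6, they are 1.1 to 8.7% and 0.4 to 4.2%.

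**Step 3: quantiles.** Medians move by at most about 2 h (control 63 to 65 h; racecadotril about 28 h throughout). The control upper quartile goes from 94 h to about 100 h at a median gap of 12 h. It is not reached at 18 h or 24 h, where 80.6×0.925 = 74.6% and 80.6×0.866 = 69.8% have events, both below 75%.

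**Step 4: log-rank test, 55 per arm, 4,000 simulated trials.** Power is about 94.5% without the loss and 93 to 94.5% with it. With no drug effect and the same gap in both arms, each one-sided error stays between 2.4 and 2.9%. Power exceeds the planned 80% because the simulation uses the whole curves with recovery as the event. The protocol's 55 reproduces from Freedman's formula with the 72 h percentages entered as survival proportions: ln 0.842/ln 0.594 = 0.330, 31.0 events, 31.0/(2−0.594−0.842) = 54.9.

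**Step 5: gap longer on racecadotril, no drug effect.** A false result favouring ORS appears in about 7% of trials (median gaps 18 h control, 24 h racecadotril) or 12% (12 h and 24 h), against 2.5% nominal.

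**The case against.** **The SAP may only be clarifying the protocol.** Protocol 8.1 dates recovery by an evacuation, and an absence of stool has none. The SAP wording, "no stool within 12 hours after first normal stool", can be read as supplying the missing anchor, and four protocol passages give only the two-normal-stools rule. This stands to the extent that a reader might infer the protocol settles the child as recovered, and it does not. The SAP's outcome for the child is the same either way.

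**SAP 3.3 may rescue the child** through the end-of-treatment alternative. On that reading, though, a child still ill on Day 6 also gets an event, and the 144 h rule has almost nobody to apply to. Section 4.2.1 governs the analysis and omits it. Figure 3-2, which illustrates both definitions, could not be seen.

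**The primary test barely moves.** This stands when the gap is the same in both arms. A reader might infer from the widened 120 h difference that the trial is biased toward a false positive for racecadotril; step 4 does not show that. A reader might also infer a large loss of power. Moving an arbitrary 10% of resolved children in each arm to 144 h does cut simulated power to about 76%. But that needs children who resolve on day 1 to be lost as often as late ones, whereas Protocol 4.1 and 8.3 keep the diary open until two normal stools.

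**The inputs are weak.** The gap distribution is assumed. The earlier study's recovery definition is not given; if it already required a normal stool, the losses are partly counted twice. Both points stand.

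**A 12 h trailing rule makes its own errors,** since 12 h before a morning visit is little more than overnight. Assume gaps between watery stools with median 6 to 10 h (log-SD 0.6). Then about 8 to 24% of still-ill children would have such a gap: roughly 1.6 to 4.6 points in control (19.4% unrecovered) and 0.4 to 1.2 points on racecadotril (5.3%). This stands, and is why a longer interval belongs in the sensitivity analyses.

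**Conclusion.** The concern holds as a defect in the definitions. Applied as written, SAP 4.2.1 scores an illness that has ended as one that has not, for any child who passes no stool after the last watery one. The SAP and protocol passages also conflict on whether that child has recovered.

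The size is not in the documents. Under the assumed gap (median 12 to 24 h), the loss is about 3 to 13% of resolved control and 1 to 6% of resolved racecadotril subjects. The 120 h difference moves from 14.1 to about 15 to 19 points, and the control upper quartile rises or is not reached. Medians and log-rank power are little affected if the gap is the same in both arms. If the drug lengthens it, the one-sided error against racecadotril could reach about 7 to 12% in the cases tried. The direction is therefore not fixed. The sponsor should correct this before lock, chiefly for the late recovery rates and the upper quartile.

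**What to change.** Reconcile Protocol 8.1 with SAP 3.3, 4.2.1 and 4.2.2 into one analysis rule for recovery and the primary event. State whether the end-of-treatment alternative in SAP 3.3 applies. Fix the rule before database lock and before anyone counts affected children by arm, since the trial is open-label.

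Suggested text for SAP 4.2.1, with a matching rule for recovery in 4.2.2: a subject whose last recorded stool is watery, followed by at least 12 hours without stool up to the end of the diary, has the primary event at that last watery stool, provided that drug, ORS or temperature entries show the diary was kept over that interval.

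The 12 h is the protocol's own interval. Because the rule looks only at the end of the record, an earlier long gap followed by another watery stool does not trigger it. Add two sensitivity analyses, one with a longer interval such as 24 h and one with the present 144 h censoring, and report the number of such subjects by arm.

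This is an analysis rule only. The passages telling caregivers when to stop treatment also need to be reconciled, but that is for the sponsor.

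The cost is SAP wording and one derivation on data already in the diary. The downside is that some still-ill children with a short trailing gap will be counted as ended; the two sensitivity analyses bound that.

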Subjects will be treated with Racecadotril tid according to the body weight dose requirement on an in- or out-patient basis for maximum 5 days. One arm will be treated with ORS alone as standard treatment, the other treatment arm will be treated with ORS (according to the registered local label and the instruction of the investigator) in addition to Racecadotril. ORS will be prescribed by the investigator and will be taken according to the product label and the instruction of the investigator. The parent(s)/caregiver(s) will be instructed to stop study drug treatment when the patient recovered. On each day, the parent(s)/caregiver(s) will fill in their diaries, documenting the date and time of each individual stool, the stool consistency of each stool (diarrheal/watery or normal), the amount of ORS and the study drug intake. After the occurrence of two consecutive normal stools, the parent(s)/caregiver(s) can stop recording of the diary and

[figure not shown]
return to the study site for the end of treatment visit. The date of recovery is the day when the first of two consecutive normal stools were excreted. AEs are to be reported on an ongoing basis.

End of treatment (Day 6 or early recovery, Visit 2)

The last dose of study drug will be the morning dose of day 6, if not recovered earlier. The same day, or within 24 hours after recovery, the parent(s)/caregiver(s) will visit the site for the end of treatment visit of the child. Data on vital signs, AEs, physical examination and concomitant medication will be collected. Subjects will return their diaries and unused medication.

Safety follow-up

A phone call will be performed at 5-7 days after end of the treatment period for the safety follow-up.

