6 REMOVAL OF SUBJECTS FROM THERAPY OR ASSESSMENT

All subjects are free to withdraw from participation in this study at any time, for any reason, specified or unspecified, and without penalty or loss of benefits to which the subject is otherwise entitled.

The Study Termination form must be completed for all subjects who did not fail screening, those who completed and those who prematurely terminated the study.

In case of premature termination of the subject from the study, the primary reason for this premature termination is to be indicated according to the following definitions:

- Adverse event: discontinuation due to any adverse event (AE) with a corresponding entry reflected on the Adverse Events form in the CRF.
- Lack of efficacy: subject fails to respond to the study drug at an acceptable level where the subject or the Investigator feels it is in the best interests of the subject to seek another treatment.
- Lost to follow-up: the subject fails to return to the study site for scheduled visits and does not respond to telephone or written attempts to contact.
- Withdrew consent: subject decides to stop his/her participation in the study for any reason other than an AE, or is unable to complete the study as described in the clinical study protocol (e.g. subject is relocating to another location).
- Administrative: the Sponsor decides to discontinue the study (either at the study site or the entire study), e.g. general safety problems leading the Sponsor to entirely stop the study.
- Protocol violation – anything which is in direct violation of the clinical study protocol (e.g. inclusion/exclusion violation).

Subjects with two consecutive temperature measurements of > 39 degrees Celsius during the study should be withdrawn from the study for further diagnosis and alternative treatments. Also subjects whose disease state worsens, e.g. dehydration or increased vomiting, should be withdrawn from the study. An end of treatment visit will be performed.

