4. STATISTICAL ANALYSIS

4.1 Subject samples

There will be five subject samples.

- The all subjects consented sample will consist of all subjects who:
 - Gave their informed consent.
- The all subjects allocated to treatment sample will consist of all subjects who:
 - Were in the all subjects consented sample; and
 - Were allocated to treatment.
- The safety sample will consist of all subjects who:
 - Were in the all subjects allocated to treatment sample; and
 - Had at least one dose of study medication administered.
- The full analysis (FA) sample will consist of all subjects who:
 - Were included in the safety sample; and
 - Had data for at least one post-baseline assessment of any efficacy measurement.
- The per-protocol (PP) sample will be defined through blind data review and will consist of all subjects who:
 - Were included in the FA sample; and
 - Did not present any major protocol violation (consideration about exclusion of patients from *the PP sample* will be performed at the Blind Data Review).

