4.2 Efficacy analysis

The *FA subject sample* will be used for the analysis of the efficacy data. Additionally, primary efficacy results analysis will be conducted on the *PP sample* as the sensitivity analysis. Descriptive statistics will be presented by treatment arm and by stratification level (Age Category) for all planned efficacy endpoints.

All analyses will be based on available data only and no missing data will be imputed.

All parameters will be summarized using descriptive statistics and listed.

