4.2.3 Other efficacy analysis

Additionally, duration of diarrhea and time to recovery will be analyzed using Cox regression model where treatment group, age group, and dosing/weight group will be included as covariates. Relative risk will be presented for each covariate with 95% confidence intervals (Relative risk is referred to as "Hazard ratio" in the output from PROC PHREG SAS procedure).

SAS code for the analysis:

PROC PHREG DATA = [dataset name]; CLASS [arm variable] (ref=[reference level]) [age group] (ref=[reference level]) [weight/dosing category] (ref=[reference level]); MODEL [time variable] * [censor variable] =

[arm variable] [age group] [weight/dosing category] / RL;

RUN;

The results of the exploratory analyses using Cox regression model will be provided in appropriate tables with the main results (see 10.1.4.1.2.1; 10.1.4.1.2.2; 10.1.4.1.5.1; 10.1.4.1.5.2; 10.1.4.2.2.1 and 10.1.4.2.2.2 table shells).

The comparisons by subgroup for GPA score success rating using Fisher exact test will be performed using the following SAS code:

PROC FREQ DATA = [dataset name];

WEIGHT [GPA frequency] / ZEROS;

TABLES [GPA yes/no level] * [Arm] / EXACT FISHER;

BY [age subgroup variable];

RUN;

If SAS code produces the "Row or column sum zero. No statistics computed for this table." output due to insufficient memory available to complete the Fisher exact computations, then the p-value should be assumed as equal 1.0000.

The results of the exploratory analyses will be provided in appropriate tables with the main results (see Table 10.1.4.2.3), no adjustment for multiplicity will be done due to the exploratory nature of analyses.

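### SAP 4.2.1 censors every subject without an event at 144 h, so a child who leaves early for an unrelated reason counts as still ill at every later event

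*SAP*

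**What the plan says.** SAP 4.2.1 starts the clock at first drug intake. The event is the last watery stool before recovery, so a subject who leaves unrecovered has no event. All such subjects "will be censored by 6 days (144 hours"). Neither the SAP nor Protocol 10.3 names an earlier censoring time.

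The rule reaches further than the primary analysis. Time until recovery and the recovery counts "will be estimated Kaplan Meier analysis as described for the primary endpoint" (SAP 4.2.2). SAP 4.2.3 adds that "duration of diarrhea and time to recovery will be analyzed using Cox regression model" and names no other censoring rule.

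SAP 4.2 also states: "All analyses will be based on available data only and no missing data will be imputed". FA membership needs one dose and this: "Had data for at least one post-baseline assessment of any efficacy measurement" (SAP 4.1). Protocol 6 foresees withdrawal for unrelated reasons, such as relocation or a sponsor decision, and for outcome-related ones, such as lack of efficacy, worsening or fever. Protocol 10.8 allows for 10% dropout.

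**The concern.** Kaplan-Meier and log-rank methods use a censored subject as at risk, and event-free, up to the censoring time. Setting that time at 144 h for someone last observed on Day 2 claims several days of observed illness for which there are no data. This contradicts the available-data rule in SAP 4.2.

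Two things are at stake. Recovery is understated in each arm, with some loss of power. And if unrelated withdrawal with a returned diary differs between arms, which is possible in an open-label add-on trial, the rule alone favours the arm with less of it.

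The number of affected subjects is limited. Diaries come back at Visit 2 ("Subjects will return their diaries and unused medication", Protocol 4.1), and the other efficacy measure is the "Global Physician Assessment at the end of treatment" (Protocol 8.1). Most outpatients lost to follow-up, where "the subject fails to return to the study site for scheduled visits" (Protocol 6), therefore leave no efficacy data and fall outside FA. Those affected are mainly in-patients, and subjects with withdrawn consent or administrative withdrawal whose diary was returned.

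**Working it through.** **Is 144 h later than any observation?** Treatment starts at noon or in the evening of Day 1 and ends with the morning dose of Day 6. On assumed clock times, 20:00 on Day 1 to 08:00 on Day 6 is 108 h, and 12:00 on Day 1 to midnight at the end of Day 6 is 132 h. So 144 h lies beyond the planned observation. For subjects followed to Day 6 this is harmless, because no event falls in the gap.

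**The plan's own figure.** From Protocol 10.8, HR = ln(0.842)/ln(0.594) = 0.330. Freedman events = (1.960 + 0.842)² × (1.330/0.670)² ≈ 31. Dividing by the mean probability (2 − 0.842 − 0.594)/2 = 0.282 and by 2 gives 55 per group, and 55/0.9 rounds up to 62. (This reproduces only with the recovery percentages entered as survival proportions, which is a separate matter.) The censoring rule does not change 62; it changes the estimates and the test.

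**Inputs for the check.** 62 per arm; event times piecewise-exponential through the five recovery percentages in Protocol 10.8; no-effect case: control curve in both arms. Assumed: observation to 114 h; unrelated dropout uniform over the first 48, 72 or 120 h. 20,000 replicates per scenario, Monte Carlo standard error about 0.15-0.25 points. Without dropout the two rules give identical results (type I error 4.7%, power 96.3%).

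**Closed form for 72 h recovery.** With dropout probability p at time D, the 144 h rule gives F(72) − p × mean[F(72) − F(D)]₊. With p = 0.10:

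- 48 h window: control 0.594 − 0.10 × 0.4130 = 55.3%; Racecadotril 0.842 − 0.10 × 0.4201 = 80.0%
- 72 h window: 0.594 − 0.10 × 0.3153 = 56.2%; 0.842 − 0.10 × 0.3035 = 81.2%
- 120 h window: 0.594 − 0.10 × 0.1892 = 57.5%; 0.842 − 0.10 × 0.1821 = 82.4%

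Subjects wrongly carried to 144 h number 62 × 0.10 × mean[1 − F(D)]. For the 48 h window that is 6.2 × 0.819 = 5.1 control and 6.2 × 0.578 = 3.6 Racecadotril.

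**Simulation, 10% per arm, all unrelated and all in FA (upper bound), control/Racecadotril:**

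| Dropout window | Carried to 144 h | 72 h recovery, 144 h rule | Power, 144 h rule |
|---|---|---|---|
| 48 h | 5.1/3.6 | 55.3/80.0% | 92.3% |
| 72 h | 4.5/2.9 | 56.3/81.2% | 94.0% |
| 120 h | 3.3/2.0 | 57.6/82.3% | 94.8% |

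Censoring at the last entry gives power of 95.9-96.3%. Type I error under the 144 h rule is 5.0-5.1%. With half the leavers in FA and the rest lost without data, 72 h recovery is 57.2/82.0 to 58.3/83.3% and power 93.3-94.7% (last entry 95.2-95.6%). With a quarter in FA, it is 58.3/83.1 to 58.9/83.7% and power 93.9-94.6% (last entry 94.9-95.0%).

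**No true effect, unrelated dropout 15% against 5%, type I error under the 144 h rule:**

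| Leavers in FA | 48 h | 72 h | 120 h |
|---|---|---|---|
| all (upper bound) | 10.6% | 8.6% | 6.6% |
| half | 6.9% | 6.3% | 5.6% |
| a quarter | 5.6% | 5.1% | 5.3% |

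Last-entry censoring gives 4.8-5.4% throughout. If only leavers without an event fall outside FA, the middle row becomes 5.9, 5.8 and 5.0%. A separate run with all leavers in FA and withdrawal over 6-72 h gave 8.3%, of which 7.6 points favoured the arm with less dropout.

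**Mixed case, 10% per arm:** 4% lost outside FA, 3% outcome-related, 3% unrelated. Counting the outcome-related leavers as not recovered, the target 72 h recovery is 57.5/81.6%.

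| Rule | 48 h | 72 h | 120 h |
|---|---|---|---|
| 144 h for all | 56.2/80.2% | 56.5/80.6% | 56.9/81.0% |
| last entry for all | 59.1/83.7% | 58.7/83.3% | 58.3/82.5% |

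Splitting by reason gives 57.5/81.4-81.5%. With unrelated dropout 4.5% against 1.5% and no effect, type I error is 5.3-5.8% under 144 h and 5.1-5.4% under the split rule.

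**Late confirmation of recovery.** If recovery is confirmed 12-24 h after the last watery stool (assumed), the 15% against 5% case gives 12.9, 11.1 and 7.5% with all in FA, or 7.1, 6.8 and 5.8% with half. Last entry gives 5.0-5.3%. With this lag and 10% per arm, all in FA, last-entry censoring puts 72 h recovery at most about 0.9 points low.

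**The case against.** The strongest case against concerns size. With balanced dropout the 72 h contrast hardly moves: in the upper-bound table it is 24.7, 24.9 and 24.7 points against a true 24.8. Power stays well above the planned 80% on the sponsor's curves. The type I error figures need a 3:1 dropout split that the documents do not give, and a strong imbalance would often reflect lack of efficacy, where counting the subject as not recovered is defensible. In the mixed case, with about 2 unrelated FA leavers per arm (62 × 3%), the type I error ranges of the two rules overlap. All of this stands and limits the severity. The power cost would be larger for a smaller effect, however: at an assumed HR of 1.6 with 10% dropout over 6-72 h, it is 59% against 66%.

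Two objections concern the text. First, the censoring phrase might mean only an upper limit; but then every early leaver's censoring time is undefined, and the paragraph still needs repair. Second, the primary objective (Protocol 3.1, SAP 3.3) measures to recovery or the end of study treatment, so an unrecovered leaver might be given an event at the last watery stool. SAP 4.2.1, which defines the analysis, stops at recovery and provides for subjects without an event, so that reading is less natural.

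The disposition table (10.1.1.1), the listing of premature terminations (12.2.1.3), the stool listing (12.2.9.3) and the per-protocol analysis would let a reader find affected subjects. None of them changes the rule.

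Finally, last-entry censoring for everyone is no improvement: in the mixed case it is up to 2.1 points high (83.7 − 81.6), against 0.6-1.4 points low for the present rule. That is correct, and it is why the fix must split by reason.

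**Conclusion.** The concern holds, and the rule should be fixed. As written it credits FA subjects who leave early for unrelated reasons with unobserved illness up to 144 h, in conflict with SAP 4.2, in the primary analysis, time until recovery and, by default, the Cox models.

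The impact is moderate to low. At the planned dropout, balanced between arms, recovery is understated by at most about 4 points per arm at 72 h, and by 0.6-1.4 points in the mixed case. A few points of power are lost and type I error is intact. Error inflation needs an imbalance in unrelated dropout with returned diaries; its size and direction cannot be known from the documents. Dropout timing, FA shares and arm splits are all assumptions.

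The point does not extend to outcome-related withdrawals, for which non-recovery is a defensible outcome, or to subjects followed to Day 6. Subjects withdrawn for fever or worsening have an end of treatment visit and so tend to stay in FA.

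**What to change.** Amend SAP 4.2.1 before database lock:

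1. Censor subjects without an event at their last diary entry; for those followed to Day 6, at the end of the Day 6 diary.
2. Keep subjects whose recorded termination reason is outcome-related as non-recovered to the end of the observation window, and list in advance which reasons count.
3. Apply the same derivation to time until recovery and to the Cox models.
4. Report 144 h for all as a labelled sensitivity analysis.

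The cost is one paragraph, one censoring derivation and one extra table. Stool times and termination reasons are already collected. The drawback is that the list of reasons must be fixed in advance because the trial is open-label. The withdrawn-consent category takes in any reason other than an adverse event, so some of its members may be outcome-related; the 144 h sensitivity analysis shows the other extreme.
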